9.5.3 Appropriateness of Measurements

All clinical assessments are standard measurements commonly used in studies of soft tissue sarcomas.

The safety assessments to be performed in this study, including hematology analyses, blood chemistry tests, urinalysis, radiologic studies, and assessment of AEs, are standard evaluations to ensure subject safety.

9.5.4 Reporting of Serious Adverse Events, Pregnancy, and Events Associated with Special Situations

9.5.4.1 Reporting of Serious Adverse Events

All SAEs, regardless of their relationship to study treatment, must be reported on a completed SAE form by email or fax as soon as possible but no later than 1 business day from the date the investigator becomes aware of the event.

Serious adverse events, regardless of causality assessment, must be collected through the last visit in the Treatment Phase, and for 28 days after the subject's last dose. All SAEs must be followed to resolution or, if resolution is unlikely, to stabilization. Any SAEs judged by the investigator to be related to the study treatment or any protocol-required procedure should be reported to the sponsor regardless of the length of time that has passed since study completion.

The detailed contact information for reporting of SAEs is provided in the Investigator Study File.

For urgent safety issues, please ensure all appropriate medical care is administered to the subject and contact the appropriate study team member listed in the Investigator Study File.

It is very important that the SAE report form be filled out as completely as possible at the time of the initial report. This includes the investigator's assessment of causality.

Any follow-up information received on SAEs should be forwarded within 1 business day of its receipt. If the follow-up information changes the investigator's assessment of causality, this should also be noted on the follow-up SAE form.

Preliminary SAE reports should be followed as soon as possible by detailed descriptions including copies of hospital case reports, autopsy reports, and other documents requested by the sponsor.

The investigator must notify his/her IRB/IEC of the occurrence of the SAE in writing, if required by their institution. A copy of this communication must be forwarded to the sponsor to be filed in the sponsor's Trial Master File.

9.5.4.2 Reporting of Pregnancy and Exposure to Study Drug Through Breastfeeding

Any pregnancy in a female subject (or partner of a male subject) in which the estimated date of conception is either before the last visit, or within 28 days of last study treatment, or any exposure to study drug through breastfeeding during study treatment or within 28 days of last study treatment, must be reported.

If an adverse outcome of a pregnancy is suspected to be related to study drug exposure, this should be reported regardless of the length of time that has passed since the exposure to study treatment.

A congenital anomaly, death during perinatal period, an induced abortion, or a spontaneous abortion are considered to be an SAE and should be reported in the same time frame and in the same format as all other SAEs (see Reporting of Serious Adverse Events [[Section 9.5.4.1](#)]).

Pregnancies or exposure to study drug through breastfeeding must be reported by fax or email as soon as possible but no later than 1 business day from the date the investigator becomes aware of the pregnancy. The contact information for the reporting of pregnancies and exposure to study drug through breastfeeding is provided in the Investigator Study File. The Pregnancy Report Form must be used for reporting. All pregnancies must be followed to outcome. The outcome of the pregnancy must be reported as soon as possible but no later than 1 business day from the date the investigator becomes aware of the outcome.

A subject who becomes pregnant must be withdrawn from the study.

9.5.4.3 Reporting of Events Associated with Special Situations

9.5.4.3.1 REPORTING OF ADVERSE EVENTS ASSOCIATED WITH STUDY DRUG OVERDOSE, MISUSE, ABUSE, OR MEDICATION ERROR

Adverse events associated with study drug overdose, misuse, abuse, and medication error refer to AEs associated with uses of the study drug outside of that specified by the protocol. Overdose, misuse, abuse, and medication error are defined as follows:

Overdose	Accidental or intentional use of the study drug in an amount higher than the protocol-defined dose.
Misuse	Intentional and inappropriate use of study drug not in accordance with the protocol
Abuse	Sporadic or persistent intentional excessive use of study drug accompanied by harmful physical or psychological effects
Medication error	Any unintentional event that causes or leads to inappropriate study drug use or subject harm while the study drug is in the control of site personnel or the subject.

All AEs associated with overdose, misuse, abuse, or medication error should be captured on the Adverse Event CRF and also reported using the procedures detailed in Reporting of Serious Adverse Events ([Section 9.5.4.1](#)) even if the AEs do not meet serious criteria. Abuse is always to be captured as an AE. If the AE associated with an overdose, misuse, abuse, or medication error does not meet serious criteria, it must still be reported using the SAE form and in an expedited manner but should be noted as non-serious on the SAE form and the Adverse Event CRF.

9.5.4.4 Expedited Reporting

The sponsor must inform investigators and regulatory authorities of reportable events, in compliance with applicable regulatory requirements, on an expedited basis (ie, within specific time frames). For this reason, it is imperative that sites provide complete SAE information in the manner described above.

9.5.4.5 Regulatory Reporting of Adverse Events

Adverse events will be reported by the sponsor or a third party acting on behalf of the sponsor to regulatory authorities in compliance with local and regional law and established guidance. The format of these reports will be dictated by the local and regional requirements.

9.5.5 Completion/Discontinuation of Subjects

A subject may elect to discontinue the study at any time for any reason. All subjects who discontinue the study are to complete the study's discontinuation procedures indicated in the Schedule of Procedures/Assessments ([Table 9](#)).

The investigator will promptly explain to the subject involved that the study will be discontinued for that subject and provide appropriate medical treatment and other necessary measures for the subject. A subject who has ceased to return for visits will be followed up by mail, phone, or other means to gather information such as the reason for failure to return, the status of treatment compliance, the presence or absence of AEs, and clinical courses of signs and symptoms.

Subjects who discontinue from the study will be discontinued for 1 of these primary reasons: AE(s), lost to follow-up, subject choice, inadequate therapeutic effect, progression of disease, withdrawal of consent, pregnancy, study terminated by sponsor, or other. In addition to the primary reason, the subject may indicate 1 or more secondary reason(s) for discontinuation. Study disposition information will be collected on the Subject Disposition CRF.

A subject removed from the study for any reason other than toxicity or progression may be replaced.

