----------------------------------	---

Platelets	Grade 4 thrombocytopenia Grade 3 thrombocytopenia requiring platelet or blood transfusion or both
Non-hematological toxicity	Grade 3 or 4 non-hematological toxicities (attributable to study drug); except Grade 3 hypophosphatemia, hypokalemia, hypocalcemia or hypomagnesemia that respond to supplementation

Table 3 Eribulin Mesylate Dose Modifications

Dose modifications based on adverse events (AEs) for eribulin mesylate (Starting dose determined by COG protocol ADVL1314/Eisai Study E7389-A001-113; 1.4 mg/m²).

Dose Level	Eribulin mesylate (mg/m²)
0*	1.4
-1	1.1
-2	0.8

* Dose level 0 refers to the starting dose.

If hematological toxicities do not recover following a dose reduction to dose level -1 and the use of hematopoietic growth factors the dose should be reduced to dose level -2. If non-hematological toxicities do not recover following a dose reduction to dose level -1, a second dose reduction to dose level -2 should be made. If either hematologic or non-hematologic toxicities do not recover despite two dose reductions, the subject should be discontinued from treatment. However, if the subject is deemed to have clinical benefit, continuation of treatment may be discussed with the sponsor.

Do not re-escalate dose after the dose level has been reduced.

Duration of Treatment

Subjects may remain on study treatment as long as they do not meet any of the following criteria: 1) experience objective progression of disease (according to RECIST 1.1); 2) exhibit no clinical benefit (in the opinion of the investigator); 3) experience unacceptable toxicity leading to withdrawal from the study; 4) withdraw or are withdrawn from the study for any reason, or; 5) termination of the study program, whichever occurs first.

As long as the subject is still receiving clinical benefit and has not experienced intolerable toxicity, he or she can continue to receive study treatment. An end of treatment (EOT) visit within 28 days after last date of receiving investigational drug will be performed for subjects who discontinue study treatment. After discontinuation of treatment and completion of the EOT visit, subjects will be followed up for survival approximately every 12 weeks for 1 year, and then annually thereafter, unless consent is withdrawn or death.

Concomitant Drug/Therapy

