9 INVESTIGATIONAL PLAN

9.1 Overall Study Design and Plan

E7389-G000-223 is a Phase 2, multicenter, open-label study to conduct a preliminary assessment of the safety and activity of eribulin mesylate in pediatric subjects with relapsed/refractory RMS, NRSTS, or EWS.

Forty-five pediatric subjects, with approximately 15 subjects each with RMS, NRSTS, or EWS, will be enrolled to receive eribulin mesylate as an intravenous (IV) infusion at a dose of 1.4 mg/m² (Recommended Phase 2 Dose [RP2D]) on Days 1 and 8 of each 21-day cycle as determined by the dose finding study ADVL1314 (Eisai Study E7389-A001-113).

Outline

- Pediatric subjects with relapsed/refractory RMS, NRSTS or EWS will be enrolled to receive therapy with eribulin mesylate.
- For each histology type, approximately 15 subjects will be treated. Data will be monitored on an ongoing basis; depending on evaluation by the investigators and sponsor, if sufficient responses (PRs or CRs) are observed, then this histology type will be recommended for inclusion in the subsequent study.
- Subjects will continue study therapy until progression of disease (per RECIST 1.1), intolerable toxicity or withdrawal of consent.

Pre-study Phase:

Day -28 to -1, computed tomography (CT) / magnetic resonance imaging (MRI) scans must be performed within 28 days prior to study drug administration. All clinical and laboratory test results to determine eligibility must be performed within 7 days prior to study drug administration, unless otherwise indicated.

Treatment Phase:

The treatment phase will start on Day 1 of Cycle 1.

Follow-up:

The follow-up period will begin immediately after the End of Treatment visit until death or informed consent is withdrawn, unless the study is terminated by the sponsor. Subjects will be followed for survival approximately every 12 weeks for 1 year and then annually thereafter. As well as follow-up for survival, the annual surveillance will also assess any long term effects of the study treatment.

During the follow-up period, subjects who have gone off study treatment without progression should have tumor assessments every 6 - 12 weeks, at the investigator's discretion, from the date of last tumor assessment until disease progression is documented, death, or initiation of

another anticancer therapy, whichever occurs first, unless the study is terminated by the sponsor. Follow-up data will be required unless consent is withdrawn.

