9.7.1.1 Study Endpoints

9.7.1.1.1 PRIMARY ENDPOINT

The primary endpoint is:

- Objective response: number of subjects achieving a best objective response of partial or complete response (PR or CR), by up to 24 weeks after all subjects have completed response assessment. Response assessment will be as determined by investigator.

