9.7.1.6.1 PRIMARY EFFICACY ANALYSIS

The primary analysis will be based on investigator assessments of tumor response.

The primary analysis is to examine the number of responders within each histology subject cohort. Confirmed response (PR or CR) will be used in this analysis. In each of the histology groups of RMS, NRSTS, and EWS, approximately 15 subjects will be enrolled and treated with eribulin mesylate. Data will be monitored on an ongoing basis; depending on evaluation by the investigators and sponsor, if sufficient responses (PRs or CRs) are observed, then this histology type will be recommended for inclusion in the subsequent study. At the latest, the primary analysis will be performed when approximately 15 subjects have completed 24 weeks of response assessments.

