9.7.3 Interim Analysis

Data will be monitored on an ongoing basis; depending on evaluation by the investigators and sponsor, if sufficient responses (PR or CR) are observed, then this histology type will be recommended for inclusion in the subsequent study.

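### The replacement rule lets a treated child taken off for lack of effect be replaced, while the cohort decision counts responders, so each such replacement adds a modest extra chance of a favourable recommendation

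*Protocol*

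**What the plan says.** **Replacement.** Protocol 9.5.5, and 9.3.3 in the same words, states that "A subject removed from the study for any reason other than toxicity or progression may be replaced". Neither section caps the number of replacements or says how a replaced child counts toward the cohort.

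**Reasons for leaving.** Section 9.5.5 gives the primary reasons for discontinuing from the study as "AE(s), lost to follow-up, subject choice, inadequate therapeutic effect, progression of disease, withdrawal of consent, pregnancy, study terminated by sponsor, or other". Lack of effect and progression are separate entries, and only progression is barred from replacement.

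**Stopping treatment.** The synopsis, under Duration of Treatment, has a related criterion for ending study treatment: "exhibit no clinical benefit (in the opinion of the investigator". It stands apart from objective RECIST progression. Under 9.3.3, a child who only stops treatment moves into follow-up and continues disease assessments.

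**Endpoint and decision.** The primary endpoint (Protocol 9.7.1.1.1) is "Objective response: number of subjects achieving a best objective response of partial or complete response (PR or CR". Section 9.7.1.6.1 adds: "The primary analysis is to examine the number of responders within each histology subject cohort". The investigators and sponsor make the decision, which 9.7.3 words (and SAP 6 repeats) as follows: "if sufficient responses (PR or CR) are observed, then this histology type will be recommended for inclusion in the subsequent study". No number, rate or denominator defines what is sufficient.

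**Size and analysis set.** Protocol 9.1 says "For each histology type, approximately 15 subjects will be treated". The total is approximately 45 in Protocol 9.3 and up to 45 in SAP 4. The Full Analysis Set holds every dosed child (Protocol 9.7.1.2, SAP 5.2.1). Missing response counts as non-response (SAP 5.3.5). SAP 5.4.1 adds the objective response rate with an exact 95% interval.

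**The concern.** A replacement rule does little harm when the reason for leaving is unrelated to outcome. Here one permitted reason is itself an outcome: the drug was judged not to be working. The child who leaves contributes no response, and the child who enters may contribute one. A count of responders can therefore stay the same or rise, but cannot fall.

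The trial is open-label and response is assessed by the investigators. They also judge lack of benefit, and they share in the evaluation of accruing responses. Enrolment would then depend partly on outcome, and any response threshold chosen later would be applied to a cohort whose size was not fixed in advance. At stake is the chance that a histology with little activity is recommended for the next study.

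**Working it through.** The plan gives no power, error rate, null response rate or numeric threshold, so there is no stated figure to reproduce.

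**Inputs from the documents.** About 15 children per histology (Protocol 9.1); a decision based on a responder count (9.7.1.1.1, 9.7.1.6.1, 9.7.3); all dosed children retained (9.7.1.2, SAP 5.2.1).

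**Assumptions.** A true response rate p of 2%, 5%, 8% or 10% stands for low activity. A bar r of 1, 2 or 3 responses stands in for the undefined threshold. The number of replacements is 1 or 3. A replaced child is a non-responder who stays in the analysis set. Responses are independent with common p.

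**Formula.** With n children treated,

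P(X ≥ r) = 1 − Σ (k = 0 to r − 1) C(n, k) p^k (1 − p)^(n − k).

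Going from n to n + 1 adds p × P(X = r − 1 among n).

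**One replacement at p = 5%, n = 15 to 16.**

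- r = 1: 0.05 × 0.95^15 = 0.05 × 0.463 = 0.023, or 2.3 points.
- r = 2: 0.05 × (15 × 0.05 × 0.95^14) = 0.05 × 0.366 = 0.018, or 1.8 points.
- r = 3: 0.05 × (105 × 0.05² × 0.95^13) = 0.05 × 0.135 = 0.007, or 0.7 points.

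**Chance of reaching the bar in one cohort (%).**

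| p | r | n = 15 | n = 16 | n = 18 |
|---|---|---|---|---|
| 2% | 1 | 26.1 | 27.6 | 30.5 |
| 2% | 2 | 3.5 | 4.0 | 5.0 |
| 2% | 3 | 0.3 | 0.4 | 0.5 |
| 5% | 1 | 53.7 | 56.0 | 60.3 |
| 5% | 2 | 17.1 | 18.9 | 22.6 |
| 5% | 3 | 3.6 | 4.3 | 5.8 |
| 8% | 1 | 71.4 | 73.7 | 77.7 |
| 8% | 2 | 34.0 | 37.0 | 42.8 |
| 8% | 3 | 11.3 | 13.1 | 17.0 |
| 10% | 1 | 79.4 | 81.5 | 85.0 |
| 10% | 2 | 45.1 | 48.5 | 55.0 |
| 10% | 3 | 18.4 | 21.1 | 26.6 |

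Across this grid, one replacement adds about 0.1 to 3.4 points.

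**Is n = 18 feasible?** Three cohorts of 18 need 3 × 18 = 54 children, above the SAP's ceiling of 45. One cohort of 18 leaves 45 − 18 = 27 for the other two. So three replacements could occur in one cohort if others fell short of 15, but not in all three.

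**The rate.** Replaced children stay in the denominator, so it is not inflated. Two responders give 2/15 = 13.3% (95% CI 1.7 to 40.5) without replacement and 2/18 = 11.1% (1.4 to 34.7) with three.

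**The case against.** Several points on the other side stand.

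- **Nobody is dropped from the analysis.** A reader might infer that replacement deletes known non-responders and inflates the response rate. The documents do not support that: every dosed child is in the Full Analysis Set, missing response is non-response, and SAP 5 asks for summary tables by histology. What remains is that extra children raise the chance of reaching a fixed count, as any enrolment beyond 15 would. The difference here is that the enrolment can be triggered by outcome.
- **Stopping treatment is not removal from the study.** A reader might also infer that the synopsis criterion on lack of benefit makes a child replaceable by itself. It concerns treatment, whereas the replacement sentence concerns removal from the study, and 9.3.3 keeps a child who stops treatment in follow-up. The case rests on the list of reasons in 9.5.5, which does refer to leaving the study. The documents never say whether stopping treatment alone counts.
- **The decision is not mechanical.** The investigators and sponsor will also have the response rate and its interval, and can read 2 of 18 as such. But neither document ties the recommendation to that rate.
- **The undefined threshold matters more.** If one response sufficed, a drug with a 5% response rate would pass 53.7% of the time with no replacement at all. The one-response rule appears only as superseded text in the revision history, so it is used here only as one illustrative bar. The missing threshold does not excuse the replacement rule: a threshold set later would still need a fixed n for its error rate to be known.

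**Conclusion.** The point holds, at modest size. The replacement sentence, read with the reasons in 9.5.5, permits replacement of a dosed child who failed for lack of effect without formal progression. The primary endpoint and the recommendation are worded as a count without denominator or threshold, so each such replacement adds a chance of a favourable count. The objective response rate is largely protected.

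The size rests on assumptions that the documents do not supply: the true response rate, the bar and the number of replacements. The most realistic illustration is a single replacement, worth about 2 points at a 5% rate with a bar of 1 or 2. The figures at n = 18 are an upper illustration for one cohort. A reader might infer that a wholly inactive drug gains from the rule. It does not: at a true response rate of zero, replacement changes nothing, so the concern applies to low but non-zero activity.

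**What to change.** 1. In Protocol 9.3.3 and 9.5.5, add inadequate therapeutic effect and absence of clinical benefit to toxicity and progression as reasons that do not allow replacement.
2. In the same sections, state that stopping treatment alone, with the child continuing in follow-up, does not trigger replacement.
3. In SAP 5.4.1 and 6, state that the responder count used for the recommendation is read against all treated children in that histology, including any who were replaced.

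Replacement for reasons unrelated to outcome can stay. Limiting it to children who were never dosed would go further than the defect requires, because it would also bar replacement of dosed children lost to follow-up or withdrawing consent.

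The cost is a few sentences across the two documents, with no change to treatment or assessments. The downside is that a cohort may have slightly fewer children with a full assessment. That is tolerable, since the cohort size is approximate and was set by clinical judgment (Protocol 9.7.2).

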9.5.6 Abuse or Diversion of Study Drug

During the study, the investigator will report any concern about abuse or diversion of study drugs by completing the Abuse or Diversion of Study Drug CRF.

Adverse events associated with abuse or diversion will be appropriately reported as AEs and monitored per [Section 9.5.1.6.1](#). Abuse is always to be captured as an AE.

During the study, the investigator should be aware of the possibility of abuse or diversion of study drugs and should report any concern about mishandling, abuse, loss, theft, or diversion of study drugs by completing the Potential Abuse-related Medication Handling Event CRF.

9.6 Data Quality Assurance

This study will be organized, performed, and reported in compliance with the protocol, SOPs, working practice documents, and applicable regulations and guidelines. Site audits will be made periodically by the sponsor's or the CRO's qualified compliance auditing team, which is an independent function from the study team responsible for conduct of the study.

9.6.1 Data Collection

Data required by the protocol will be collected on the CRFs and entered into a validated data management system that is compliant with all regulatory requirements. As defined by ICH guidelines, the CRF is a printed, optical, or electronic document designed to record all of the protocol-required information to be reported to the sponsor on each study subject.

Data collection on the CRF must follow the instructions described in the CRF Completion Guidelines. The investigator has ultimate responsibility for the collection and reporting of all clinical data entered on the CRF. The investigator or designee as identified on Form FDA 1572 must sign the completed CRF to attest to its accuracy, authenticity, and completeness.

Completed, original CRFs are the sole property of Eisai and should not be made available in any form to third parties without written permission from Eisai, except for authorized representatives of Eisai or appropriate regulatory authorities.

